Figure 2: A) BRAF^{V600E} level is higher ($p < 0.0001$) in patients with tissue-detected BRAF mutation than in patients with Stage IV BRAF WT melanoma, and patients without melanoma (normal); B) BRAF^{V600E} level is borderline significantly higher ($p = 0.10$) among patients with Stage IV, BRAF mutant melanoma than in patients with Stage II and III melanoma with a "positive" BRAF level (≥ 10 pg).

In practice, the assay is highly sensitive and specific when used to analyze isolated PBMCs from patients with Stage IV melanoma. In particular, the sensitivity and specificity of the assay, using a cut off for positivity of 10 pg, is 93% and 100%, respectively (Figure 2A shows the box plot of BRAF values in patients with melanoma and known tissue BRAF status or people without melanoma). The average BRAF level in stage IV melanoma patients with tissue confirmed BRAF mutation is higher than the average BRAF level in patients with Stage II and III patients who have a positive blood BRAF level using the cutoff of ≥ 10 pg (Figure 2B), suggesting that the assay may reflect tumor burden. Lastly, when patients on BRAF inhibitor therapy were followed with serial sampling, the assay is reflective of disease response and disease progression. Specifically, BRAF levels generally reduce with treatment initiation and then increase at the time of or, in many cases, prior to radiographic progression.

[figure not shown]

Figure 3: Mean values of BRAFV600E levels prior to (PRE), during the first cycle(C1), or at the beginning of subsequent treatment cycles (C2-C7) in 12 patients treated with vemurafenib (A) and 6 patients treated with the combination of dabrafenib and trametinib (B).

A first generation peripheral blood BRAF assay had been utilized to follow serial circulating BRAF levels in several patients treated with either vemurafenib or the combination of dabrafenib with trametinib. In each patient, who had a known BRAF mutation detected in tissue from a CLIA approved laboratory, peripheral blood BRAF levels were

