Fig 5. Incidence of grade 3-4 AEs. From Sznol et al: "Pooled Analysis Safety Profile of Nivolumab and Ipilimumab Combination Therapy" (5). The percent of patients who experienced at least one grade 3-4 irAE at the respective times (total n=448) are shown [from the original Figure in Ref. (5)]. **Arrows:** time points of **blood collection** in the current study.

Statistical Design and Analysis Plan

Sample Availability Assessed as of July 2020

Overall 90% of the patients consented to participate in the correlative study. We summarized inventory for patients enrolled as of 12/31/19 (as our assessment requires at least 24 weeks of follow-up time) and projected the numbers for the remaining patients.

Aim 1a: Based on the data as of 12/31/19, 90% of the enrolled patients consented to participate in the correlative study. Of the consented patients, 90% had baseline samples and 86% (of the cases submitted baseline samples) had samples on at least one FU time point. At the completion of the study, approximately 104 patients (150X.9X.86) will provide samples for the analysis proposed in Aim 1a. The crossover rate (to arm C or D) was lower than anticipated, but could not be assessed accurately at this point as the study is still being conducted. We project at least 46 patients crossed over to arm D will provide samples for Aim 1a. Therefore, the overall sample size for Aim 1a will be approximately 150 patients.

Aims 1b and 2: As of 12/31/19, approximately 50% of the patients in arm A or D had grade 3 or higher irAEs and submitted samples. Therefore, we project approximately 75 patients will have consented and submitted irAE samples when accrual is completed. The remainder of subjects with less toxicity (~75) will serve as controls.

Study Design and Analysis

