Aim 1: (a) We will first correlate the ctDNA analyses with clinical measurements of treatment responses and efficacy. Changes in the ctDNA measure from the baseline will be compared between the responders and non-responders. The relative abundance of ctDNA will be measured at each time point (baseline, weeks 6, 12, 18 and 24) by $[\text{ctDNA} / (\text{ctDNA} + \text{wtDNA})]$, resulting in a number between 0 and 1. The difference in the relative abundance of ctDNA between post-treatment time point (weeks 6, 12, 18 and 24) and baseline will be evaluated. The difference will range from -1 to 1. The difference of > 0 will be considered as a positive change (change = yes) and the rest will be considered as no change.

The initial analysis will be based on week 12 samples as these will be available on the majority of patients. Scan reports out to 24 weeks and if necessary blood samples out to the same time will be used to attempt to distinguish temporally related discrepancies. Changes in ctDNA measurements between pre- and post-treatment will be compared in responders vs. non-responders. For the primary endpoint, we first present a power calculation based on a binary formulation of ctDNA and then as a continuous measure.

Of the 150 patients treated with Ipi/Nivo, it is assumed 90 (60%) patients will achieve a response. It is hypothesized that a larger proportion of responders will have changes in ctDNA measurement after treatment. If the difference in proportion of patients with changes in the pre- and post-treatment ctDNA measurements among responders vs. non-responders is at least 25% (such as 55% vs. 30%, 65% vs. 40%, 75% vs. 50%), the sample size of 90 responders and 60 non responders will provide at least 82% power. This is based on Fisher's exact test with a two-sided type I error rate of 0.05. The distribution of changes in the ctDNA measure between pre- and post- time points will be evaluated and compared between the responders and non-responders. If the standardized difference between the responders and non-responders are at least 0.5, there will be at least 85% power based on the two-sample t-test. We will evaluate the distribution of the changes. If non-parametric test is more appropriate, Wilcoxon's rank-sum test will be used to compare the difference in the changes.

(b) Tumor status can be monitored during the course of the treatment or an irAE by quantifying the amount of tumor specific DNA (mutant ctDNA) in the blood and that prolonged

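### Aim 1(a) of the ctDNA substudy: the 82% power counts patients with any follow-up sample although the test uses week 12, and Arms A and D are pooled without stratification

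*Combined protocol and SAP*

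**What the plan says.** All of this is in Appendix XVI, Statistical Design and Analysis Plan.

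- **Counting rule.** Under Sample Availability, 90% of patients consented, 90% of those had a baseline sample, and 86% of those with a baseline sample "had samples on at least one FU time point". This leads to about 104 Arm A patients.
- **Arm D.** "We project at least 46 patients crossed over to arm D will provide samples for Aim 1a". The two counts are added to give about 150. The text notes that crossover was running below expectation and could not yet be assessed accurately.
- **Time point.** "The initial analysis will be based on week 12 samples as these will be available on the majority of patients".
- **Power.** With 60% of the 150 assumed to respond, "the sample size of 90 responders and 60 non responders will provide at least 82% power" for a 25-point difference in the proportion with ctDNA change (55 vs 30, 65 vs 40 or 75 vs 50%). "This is based on Fisher's exact test with a two-sided type I error rate of 0.05". A second statement gives at least 85% power for a standardized difference of 0.5 by t-test, with Wilcoxon's rank-sum test as the fallback. None of these tests has an arm or line-of-therapy term.
- **Discrepancies.** After naming week 12, the plan says that scans to week 24 will be used and, if needed, "blood samples out to the same time will be used to attempt to distinguish temporally related discrepancies". It defines neither a discrepancy nor what happens to a patient who has one.

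**The concern.** The sample size and the test refer to different sets of patients. A patient with a baseline and a week-6 sample but nothing at week 12 counts towards 150 and cannot enter the week-12 comparison. The stated power has little margin, so the gap matters if it is more than a few per cent.

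Pooling raises a second question. Arm D patients reach immunotherapy after dabrafenib/trametinib. Section 1.9 treats it as conceivable that they benefit less from it. Section 11.3.3 reports, for a different blood assay in patients on BRAF inhibitors, that "BRAF levels generally reduce with treatment initiation and then increase at the time of or, in many cases, prior to radiographic progression". Both the response rate and the ctDNA course could therefore differ by arm, and a single unstratified 2x2 table would mix that difference with the association of interest.

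At stake is how to read the substudy's primary hypothesis: the power quoted for it, and whether a result, positive or null, reflects ctDNA and response within a line of therapy.

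**Working it through.** **Inputs (Appendix XVI).** Two-sided alpha 0.05, Fisher's exact test, 90 responders and 60 non-responders, the three 25-point scenarios above. Week-12 availability is not given, so a range is assumed.

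**Step 1: the count.** The product printed in the appendix, 150 x 0.9 x 0.86, is 116.1. Adding the baseline-sample factor given in the text, 150 x 0.9 x 0.9 x 0.86 = 104.5. So 104 follows from the text although the printed product omits a factor, and 104 + 46 = 150. The 0.86 is the any-follow-up rate, not a week-12 rate.

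**Step 2: reproduce the plan's power.** Power is the sum, over all pairs of binomial outcomes, of their probability where the Fisher p-value is at most 0.05. At 90 vs 60:

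| Two-sided p-value | 55 vs 30 | 65 vs 40 | 75 vs 50 |
|---|---|---|---|
| Doubled one-tail | 83.1% | 82.4% | 84.4% |
| Minimum-likelihood | 85.9% | 84.1% | 86.0% |

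The lowest value, 82.4%, matches the stated figure. The t-test at d = 0.5 gives 84.6%, which rounds to the stated 85%.

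**Step 3: count only baseline and week-12 pairs.** The 60/40 split is kept. Fisher figures are the lowest of the three scenarios, doubled-tail to minimum-likelihood.

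| Pairs (share of 150) | Fisher | t-test |
|---|---|---|
| 150 (100%) | 82.4-84.1% | 84.6% |
| 144 (96%) | 80.0-82.3% | 83.2% |
| 142 (95%) | 79.8-81.4% | 82.7% |
| 135 (90%) | 77.3-78.0% | 80.7% |
| 120 (80%) | 72.0-74.5% | 75.8% |

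The 82% tolerates a loss of about 4% under one p-value convention and almost none under the other. To end with 150 pairs, the plan would need 150/0.9 = 167 patients at 90% availability or 150/0.8 = 188 at 80%.

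**Step 4: response window.** The Number of subjects paragraph expects about 50% responders by week 12 and 60% by week 24, so the 90/60 split uses the week-24 share. A 75/75 split gives at least 85.4%. The choice of window does not lower power, but it is not stated.

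**Step 5: pooling 104 Arm A with 46 Arm D, with no association inside either arm.** All arm-specific rates are assumptions.

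- Response 60% in both arms, change 50% (A) vs 30% (D): no spurious difference; simulated rejection rate 4.7%.
- Response 65% vs 49%, change 50% vs 35%: about 2 points; 5.0%.
- Response 70% vs 37%, change 60% vs 30%. Responders: (72.8 x 0.6 + 17.0 x 0.3)/89.8 = 54%. Non-responders: (31.2 x 0.6 + 29.0 x 0.3)/60.2 = 46%. About 9 points in the hypothesized direction; 17%.
- Response 60% vs 30%, change 30% vs 60%. Responders: (62.4 x 0.3 + 13.8 x 0.6)/76.2 = 35%. Non-responders: (41.6 x 0.3 + 32.2 x 0.6)/73.8 = 43%. With change 80% in Arm D: 39% vs 52%. Both run against the hypothesis, so pooling would mask a true association.

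Pooling can therefore act in either direction, and does little unless both rates differ clearly by arm.

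**The case against.** The case for leaving the plan alone has four parts.

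- **The 82% is arithmetically correct, and no week-12 rate is given.** True. The Arm D figure is also a minimum, so extra crossover patients could make up some of the loss. The shortfall is conditional. What stands is that the plan's n is not the n of its test.
- **The case that the arms differ is thin.** Section 1.9 speaks of possibility, not expectation. The finding in Section 11.3.3 comes from an RT-PCR assay on blood mononuclear cells, while Appendix XVI uses a mutation panel on serum cell-free DNA. Section 7.2 also provides a sample at crossover, so Arm D can have its own baseline. All of this is fair. It leaves the size of any bias unknown, but it gives no reason to omit the arm from the test.
- **The discrepancy sentence need not mean re-scoring.** A reader might infer that patients whose ctDNA and scan disagree are reclassified until they agree, which would inflate the association. The documents do not say so. They do not state that any class is changed or that later values enter the Fisher test, and the sentence fits late responders counted by week 24. It is an undefined rule, not a described bias.
- **The work is exploratory.** Section 2.6 labels it so, and the primary 2-year survival analysis is untouched. That limits the importance of the point, but the appendix still states a primary hypothesis and a power for it.

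**Conclusion.** The point holds in a limited form. The stated power of at least 82% applies to 150 patients with a baseline and week-12 pair, but the plan counts 150 on a looser rule. Lowest power is 77-78% if 90% have the pair and 72-75% if 80% do. Those availability rates are assumed, the 60/40 response split is kept, and the Arm D floor of 46 may be exceeded. It would be too strong to say that the planned power will not be reached, because the documents give no week-12 rate.

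The unstratified pooling of Arms A and D is a weakness of unknown size and direction. A reader might take it as a route to false confirmation of the hypothesis, but the documents give no arm-specific rates, and plausible assumptions produce a spurious association, a masked one, or practically neither. The discrepancy wording needs a rule but does not by itself show inflation.

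**What to change.** 1. Restate n and power from the number of patients with both a baseline and a week-12 sample, by arm. For Arm D, say which baseline defines change: the crossover sample or the one before dabrafenib/trametinib.
2. Replace the pooled Fisher test with an exact Mantel-Haenszel test stratified by arm, and the pooled t-test or rank-sum test with a stratified Wilcoxon test.
3. As a clarification, state that week-12 ctDNA and one response window apply to every patient in the primary test. Use later scans and blood samples for all patients in a sensitivity analysis, and not to reclassify those whose results disagree.

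The cost is SAP wording and a slightly lower stated power. No new samples or visits are needed.
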